### *Testing*

The aggressiveness of the caged mosquitoes during the test day will be determined from the landing rate on the control's arm before each test exposure. Once the landing rate has been confirmed (5 landings in 60 seconds) the counts will cease. The landing rate verification will be conducted before each exposure of the treated test subjects. If fewer than the required number of mosquitoes land in 60 seconds, a new group of 100 mosquitoes will be released into all of the cages.

The study director or technician will assist the test subjects in inserting their arms into the test cages, taking care not to rub them on the cloth sleeve. The test subjects will expose their treated forearms to the mosquitoes in these test cages for 5 minutes. The subjects will then remove their arms from the cages with assistance from an ICR staff. Exposures to the mosquitoes will be repeated every 30 minutes until the formulation on any given forearm is determined to be no longer effective or until 8 hours have elapsed, whichever occurs first.

The test data to be recorded will be bites (blood is ingested, as evidenced by abdominal swelling and color change). Test data will be recorded on a Repellency Test Data Sheet.

### *Criteria for Test End Point*

Efficacy will be evaluated by intermittent exposure of the test subjects' arms. The treated test subjects will expose their treated arms to the caged mosquitoes for 5 minutes at approximately 30 minute intervals. The test subjects will expose treated arms until the FCB (when two bites occur on the same arm in the same exposure period, or one bite occurs in each of two consecutive exposure periods, the first bite being the confirmed bite) or until 8 hours have elapsed, whichever occurs first. For the purposes of this test, a bite is defined as a mosquito penetrating the skin with its proboscis and taking sufficient blood to cause its abdomen to swell. When the two bites have occurred as noted above, the test will terminate on that arm.

When the testing is terminated for an arm, test subjects will then roll down their sleeves to cover such discontinued arms. The test will be terminated on a treated arm when a bite is followed by one additional bite (the initial bite and one confirming bite). If the bites do not occur within the specified time, the number of bites required will begin anew.

Once a confirmed bite occurs, the test subjects will stop exposing that arm to mosquitoes. They will then be able to remove the bandages and tape, scratch and wash that arm. If they want to, they can use rubbing alcohol to help stop the itching from the bites they may have received. Caladryl® or Calamine® lotion may also be used.

### **CONFIDENTIALITY**

The information obtained from test subjects taking part in this test may be used by ICR and its sponsor and may become part of a report. This report will be kept as confidential as possible under local, state and federal law. The test subjects' first and last initial and their dedicated identity number only may be referenced. ICR cannot guarantee that their identity will be kept confidential. Essex Institutional Review Board has the right to review their records.

### **DATA ANALYSIS:**

The purpose of this study is to examine the effective duration of an insect repellent. Ideally, it is expected that there will be no significant breakdown in efficacy of the product over a 8 hour interval. Given the small sample size ( $N = 10$ ) and the dichotomous nature of the data (effective vs. non-effective), nonparametric statistics will be used to analyze the data. Data will be analyzed using SPSS for Windows version 12.

Subjects will be evaluated each half hour over the 8 hour window of the study to determine whether or not the product continued to prevent insect bites. For each 30 minute assessment interval, the proportion of subjects not having insect bites will be identified. A basic degradation curve can then be plotted. These data will then be subjected to a Cochran Q test, which is particularly useful for measuring changes in frequencies (proportions) across time. A significant effect would indicate that there was a systematic degradation in the product's efficacy over the 8 hour testing interval. If such an effect is found with the Q test, then a series of 2 (baseline vs. assessment interval) X 2 (protected vs. non-protected) cross-tabulations will be created and the resulting proportions will be analyzed using a Fischer's Exact Test (employing a 1-tailed alpha level) to determine the specific time point at which efficacy became significantly impaired.

Data also to be collected from subjects will be the length of time before a significant number of bites were noted. These data will be aggregated and basic descriptive statistics determined (e.g., mean, standard deviation, confidence intervals). If this distribution is non-normal, appropriate transformations will be applied and statistics recalculated. In the case of negative skewness (which is expected), the data will be reflected and a logarithmic transformation will be employed. In the case of significantly skewed distributions, the median will be used as the measure of central tendency. Confidence intervals will be calculated on the basis of percentile ranks rather than standardized scores.

QAU AND DATA ARCHIVING

Good Laboratory Practices, as outlined in 40 CFR §160 will be followed throughout the study. The QAU representative will observe and write phase report(s) for this study. All data will be archived.

SCHEDULE OF EVENTS

DATE	PROCEDURE
Time Zero	Test Conducted
At End of Test	Verbal Report
After The Laboratory Test Conduct	Written Report

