**Exclusion Criteria:**

1. Test subjects can not participate if they are pregnant or breastfeeding.
2. Test subjects can not be an employee or a relative of an employee of ICR Inc., the sponsor, or any interested party.
3. Test subjects must follow the requirements of the study as explained to them.
4. Test subjects must not be sensitive to mosquito bites.
5. Test subjects must have no known sensitivity to insect repellents or skin care products.
6. Test subjects must be attractive to mosquitoes, as evidenced by previous being bitten by mosquitoes.
7. Test subjects must not smoke or drink alcoholic beverages 12 hours prior to the test.
8. Test subjects must not use perfumed cosmetics, skin creams, shaving lotions, etc. after 12 AM before the test, and during the test.
9. Test subjects must wear proper protective clothing during the test, such as their own blue jeans, heavy socks, long sleeve shirts, and gloves provided by ICR.

*Number of Subjects and Rationale for Sample Size*

The EPA Guideline (EPA/OPPTS Guideline 810.3700) recommends at least six test subjects be used. Because of the cost of doing repellent studies, it is prudent to ensure data collected will give a good representation of the repellency of the test formulations. In a published paper the number of subjects required to achieve an estimated among-subjects standard deviation for specific times of 0.5 hours to 2.0 hours was calculated for protection times from 1 hour to 8 hours. The number of subjects required to achieve an estimated among-subjects standard deviation of 2.0 hours at a 95% confidence level for an 8 hour protection time was calculated to be between 10 and 11 subjects. This study, therefore, will use ten treated test subjects. There will be an additional control subject, plus two additional treated test subjects to replace anyone that either drops out or is ineligible to participate due to a positive pregnancy test or other unforeseen circumstances. These additional two treated test subjects will help to ensure a minimum "n" of ten and will aid in protecting the privacy of any dropouts.

---

 L.C. Rutledge and R. K. Gupta, 1999, Variation in The Protection Periods of Repellents on Individual Human Subjects: An Analytical Review, Journal of the American Mosquito Control Association, 15(3):348-355

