## **METHODS**

### *Experimental Design*

This is a subject-blinded study. The delineated areas on the arms of subjects will be treated and used as test areas. Only arms are being treated in this study, since arms are quite easy to monitor for mosquito activity. Therefore there will be twelve test arms for each treatment. Each test

subject will have one arm treated with one of the two test products and the other arm will be treated with the other test product.

*Test location:*

This test will be conducted in the insectary at ICR. The insectary is maintained at 70% RH  $\pm$  15% RH and 70° F  $\pm$  15°F.

*Dose*

The Standard application rate of 1.67 mg/cm^2 for this study. This is the dose currently recommended in the EPA guidelines for mosquito efficacy testing and the dose that was used when the efficacy field tests were conducted on these two EPA registered products.

*Blinding of the Study*

The test articles will be coded as "A" and "B". During the test these codes will be the only test article designation referred to or that the test subjects will see. The Study Director and members of the ICR staff will know the actual test articles, but will refrain from such identifications in the presence of test subjects.

*Treatment Groups*

There will be two groups: a treated group of twelve (two more than required to allow for drop outs) subjects whose arms will be treated, and one untreated (control) test subject whose arms will be untreated. Subjects will be given a subject number. They will be assigned to the groups by lottery selection of the subject number.

*Personnel preparation*

All test subjects will complete and will sign an "Informed Consent Document" prior to acceptance as a test participant.

Females will be required to perform an over the counter pregnancy test that will be supplied by ICR. They will do this the morning of the test. The results will be verified by a female ICR staff member. They may not participate if they are pregnant or breastfeeding. The results of this pregnancy test will be kept confidential and will not be disclosed to anyone other than the test subject and the P. I.

All test subjects will wash their arms with unscented Neutrogena® soap. The test subject's arms will then be measured in the following manner for the demarcation of the 250 cm^2 test area:

*For Arms:*

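### The Cochran Q and Fisher sequence does not fit arms that leave the test at failure, so the reported time of impairment is set by sample size

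*Protocol*

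**What the plan says.** The Data Analysis section fixes a two-step procedure. The response is bite-free or not at each half-hour: "For each 30 minute assessment interval, the proportion of subjects not having insect bites will be identified". The first step is an overall test across time: "These data will then be subjected to a Cochran Q test, which is particularly useful for measuring changes in frequencies (proportions) across time". A significant result is to be taken as systematic loss of efficacy over the 8 hours. Only then does the second step follow: "a series of 2 (baseline vs. assessment interval) X 2 (protected vs. non-protected) cross-tabulations will be created". These tables are tested with a one-tailed Fisher exact test "to determine the specific time point at which efficacy became significantly impaired". No alpha value and no minimum protected proportion is given. The hoped-for result is worded as an expectation: "it is expected that there will be no significant breakdown in efficacy of the product over a 8 hour interval".

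Criteria for Test End Point ends observation of an arm at failure: "Once a confirmed bite occurs, the test subjects will stop exposing that arm to mosquitoes". The Data Analysis section does not say how the later intervals of such an arm are coded. In Appendix I, the treated-arm raw data sheet begins at 0.5 h; only the control sheet has a time 0.

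On numbers, the sample-size section says "This study, therefore, will use ten treated test subjects", and Experimental Design says "Therefore there will be twelve test arms for each treatment", the extra two being cover for dropouts. The Data Analysis section also plans a plotted degradation curve and descriptive protection-time statistics: mean or median, SD and confidence intervals.

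**The concern.** Three features of the tests clash with the design.

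- **Fisher's test assumes independent groups.** Here the baseline row and the later row of each 2×2 table hold the same arms.
- **The baseline appears to carry no data.** Treated arms have no time-0 record, so unless baseline means the first recorded interval, each table compares observations with an assumed 100%.
- **Cochran Q needs a full row of responses per arm.** Failed arms stop being exposed. Complete-case analysis loses nearly all of them. Carrying failure forward turns each such row into a run of protected followed by a run of failed, which is not the exchangeable pattern that Q assumes under its null, and the p-value then depends on how failures cluster in time.

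At stake is the inferential output named in the plan, the time at which efficacy is declared impaired. The hypothesis is 8 hours of protection, and the study is meant to support a label claim. If that time is simply when enough arms have failed for a small-sample test to cross its threshold, it measures the sample size as much as the product.

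**Working it through.** The protocol gives no figure for this procedure, so there is none to reproduce.

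**Inputs.** n = 10 analysed per product, or 12 if nobody drops out (sample-size section; Experimental Design). One-tailed test (Data Analysis). Alpha is not stated: 0.05 is assumed, with 0.025 and 0.10 as a range. There are 16 half-hourly intervals from 0.5 to 8 h (Appendix I), or 17 columns with a time-0 baseline.

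**Step 1: Fisher.** With n of n protected at baseline and k failures later, the one-tailed p is C(n,k)/C(2n,k).

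| k failed | n = 10 | n = 12 | Exact paired test, 0.5^k |
|---|---|---|---|
| 1 | 0.500 | 0.500 | 0.500 |
| 2 | 0.237 | 0.239 | 0.250 |
| 3 | 0.105 | 0.109 | 0.125 |
| 4 | 0.043 | 0.047 | 0.0625 |
| 5 | 0.016 | 0.019 | 0.031 |

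For example, C(10,3)/C(20,3) = 120/1140 = 0.105 and C(10,4)/C(20,4) = 210/4845 = 0.043. At 0.05 the fourth failure triggers a declaration at either n. At 0.10, 3 of 10 still go undeclared; at 0.025, 4 of 10 do. The same count of 3 is 30% of 10 arms but 25% of 12, so the tolerated fraction rises as n falls. An exact paired (McNemar) test needs 5 failures, so correcting for pairing alone does not help.

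**Step 2: how often the Fisher step stays silent.** If the true 8-hour failure rate is 25%, P(at most 3 failures) is 0.776 for n = 10 and 0.649 for n = 12. At 30% it is 0.650 for n = 10. These figures describe the Fisher step only.

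**Step 3: Cochran Q with failure carried forward.**
- One failing arm, 17 columns: Q = 16 on 16 df, p = 0.45, whenever it fails. With 16 columns, Q = 15 on 15 df, p = 0.45, except that failure in the first interval makes the row constant and Q = 0.
- Two failures, 17 columns: p = 0.010 if simultaneous, up to 0.39 if scattered.
- Three failures, 17 columns: p from 0.00005 if simultaneous to about 0.16 if scattered.

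The same number of failures can therefore be significant or not, depending on clustering.

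**Step 4: agreement between the two steps.** Simulation with constant hazard, 16 intervals, n = 10, failures carried forward and alpha 0.05: among trials with exactly 3 failures, Q is significant in about 73%. Fisher, at p = 0.105, names no time in any of them. With 2% risk per exposure (0.98^16 = 72% protected at 8 h), Q is significant in 53% of trials. About 26% of all trials combine a significant Q with at most 3 failures, so about half of the significant-Q trials would report degradation with no impaired time point.

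**Step 5: complete-case alternative.** An arm has a full row only if it survives or its failure is confirmed at the 8.0 h exposure. Nearly all failed arms drop out, though not necessarily every one.

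**Step 6: what estimation would show.** Exact one-sided 95% lower bounds on the 8-hour protected proportion: 10/10, 0.05^(1/10) = 0.741; 9/10, 0.606; 12/12, 0.05^(1/12) = 0.779. With 7 of 10 protected, the outcome Fisher leaves undeclared, the two-sided exact 95% interval is 0.35 to 0.93.

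**The case against.** The best defence is that Fisher is not the only place where failure would show. A significant Q is itself an adverse conclusion under the plan, and at a 25% failure rate Q is significant in about 47% of simulated trials. The planned bite-free proportions would show 3 failures in 10 as 70% protected, and the protection-time summary, which answers the stated objective of mean protection time, would reflect them too. This stands, and it limits the harm. It does not make either test valid, nor does it withdraw the breakdown time they are meant to produce.

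Some stronger readings are tempting but unsupported:

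- *That the protocol counts non-significance as success.* The text voices an expectation and sets no pass rule.
- *That at a 25% failure rate there is a 78% chance of a clean result.* That figure covers only the Fisher step; Q may already have signalled degradation.
- *That baseline is certainly a constant.* The protocol does not define it. The data sheet suggests an assumed 100%, but the first recorded interval is a possible reading.
- *That every treated-arm series is absorbing.* A single unconfirmed bite does not end testing; only the confirmed bite does.
- *That the 53% under constant hazard is a false-alarm rate.* Protection really falls to 72% in that scenario.

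It is also fair to say that the tolerance of 3 failures comes mainly from small n. That is a reason to estimate instead of swapping in another test.

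**Conclusion.** The point holds as a mismatch between a written method and the design, not as missing detail. The time of impairment depends on reaching 4 failures at n = 10 or 12, given an assumed one-sided 0.05 and 100% protection at baseline; 3 failures go undeclared throughout the range 0.025 to 0.10 at n = 10. Q and Fisher can give opposing messages from the same data. The 73% rests on constant hazard and failures carried forward, a coding the protocol does not specify.

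A reader might infer that the plan is a rule for passing a product with 30% failures. The documents do not support that, because no pass rule is written and the planned descriptive results would reveal the failures. What does follow is that a non-significant result at this sample size should not be cited as evidence of 8-hour protection. Severity: should-fix.

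**What to change.** Delete the Cochran Q and Fisher steps from the Data Analysis section. For each product separately:

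- report the Kaplan-Meier curve of arms without a first confirmed bite, with pointwise 95% limits;
- report the 8-hour proportion protected with its exact one-sided 95% lower bound;
- read protection duration from that curve, alongside the protection-time summary already planned.

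With no dropouts and a common 8-hour limit, the curve is simply the proportion of arms without a confirmed bite at each time, so the substantive addition is the confidence limits. The change costs wording only: the data are already collected, and no subjects, exposures or procedures are added. The drawback is that the stated conclusion becomes less favourable, because even 10 of 10 protected supports no more than a 74% lower bound.

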### HYPOTHESIS

The repellent samples are expected to provide 8 hours of personal protection from *Culex quinquefasciatus* mosquitoes, a West Nile virus vectors, in the laboratory.

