### OBJECTIVE

The objective of the study is to determine the mean protection time from bites provided by the test articles under laboratory conditions to confirm the hypothesis. Therefore ICR will conduct a laboratory study to assess repellency of these test articles against *Culex quinquefasciatus* mosquitoes.

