### STUDY RATIONALE

This laboratory cage study is intended to evaluate the efficacy of two currently EPA registered picaridin-containing insect repellent products (EPA Reg. No. 806-29 and 806-31) against laboratory raised *Culex quinquefasciatus*. It is well documented that *Culex* sp. are known as primary vectors of West Nile virus (WNV) in the wild. This is in contrast to the lab, where disease transmission is not possible since laboratory raised mosquitoes have never been exposed to any arboviruses. Based on this reasoning, the EPA has recommended that laboratory data with uninfected mosquitoes can be used to support the addition of WNV product label claims. Therefore, this laboratory cage study (utilizing disease free mosquitoes) is being specifically conducted to support additional label claims that the above EPA registered products repel mosquitoes that may transmit West Nile virus.

Presently there are 15 picaridin-based insect repellent products registered under FIFRA. The products range from 5% picaridin to 20% picaridin and include pump spray, aerosol, lotion, and towelete applicator products. ICR has previously evaluated Picaridin-based repellents in both the laboratory and in the field for efficacy. We have found these types of repellents to be efficacious against other species of mosquitoes in the laboratory as well as in field studies for up to and beyond 8 hours. In previous studies we have seen no indication of any type of reaction from these repellents, or cause for concern regarding safety issues.

Laboratory studies, such as the one proposed, have been considered by regulatory authorities and the scientific community to be a reliable method for testing the performance of a topically applied insect repellent product. Under FIFRA, EPA requires submission of such human efficacy study data (EPA/OPPTS Guideline 810.3700) in support of insect repellent product registration. Each new insect repellent formulation must have performance studies conducted on human subjects to substantiate the product label claims.

Each product is unique and will provide different protection times for different pests depending on both its percent active ingredient and formula composition. The incorporation of film formers, fragrances, and other ingredients may significantly influence the duration of repellency against target pests.

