While there is obviously an economic incentive to the sponsor of the study to offer a new insect repellent alternative to consumers, such products must offer a recognized benefit to consumers or they will simply not be purchased or used. It is important to bring new insect repellent products to market so that consumers have alternatives that they find personally acceptable and convenient to use to protect themselves and family members from irritating and potential disease-carrying insect bites. New products, such as the proposed test samples, have been formulated to provide protection from insect bites in combination with other benefits that promote consumer acceptance and use of the product (i.e., convenience of product form or method of application, fragrance preferences, preference for, or avoidance of, a specific active ingredient, etc.).

ICR prefers to evaluate repellency based on protection from bites rather than landings while conducting laboratory studies. Disease transmitted by laboratory raised mosquitoes that have not been exposed to any arboviruses is not possible. Therefore there is no risk of disease transmission to any of the test subjects.

In this study efficacy is defined as the Protection Time (PT). The PT is the time interval between the application of the repellent and the First Confirmed Bite (FCB). A bite is defined as the ingestion of blood by a mosquito while it is on a repellent-treated area of skin, as evidenced by an enlarged, blood filled abdomen of the mosquito. The FCB is a bite which is followed by another bite within 30 minutes.

This study may be submitted to EPA to support an insect repellent label claim. The efficacy study will test the repellent formulations in controlled laboratory conditions, exposing test subjects to only disease-free mosquitoes.

According to the EPA OPPTS Guideline No. 810.3700 "Product Performance of Skin-Applied Repellents of Insect and Other Arthropods", there exists no alternative to evaluating topical repellents on human subjects; therefore, field or laboratory testing of repellents is necessary.

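### Protection-time summaries do not treat arms still protected at 8 h as censored, so the mean protection time named in the objective cannot be validly estimated

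*Protocol*

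**What the plan says.** The Objective section sets the target: "The objective of the study is to determine the mean protection time from bites provided by the test articles under laboratory conditions". Study Rationale defines the quantity: "The PT is the time interval between the application of the repellent and the First Confirmed Bite (FCB". Under Testing, exposures are repeated "until the formulation on any given forearm is determined to be no longer effective or until 8 hours have elapsed, whichever occurs first", and Criteria for Test End Point repeats the 8 h limit.

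The expected duration sits on that limit. The Hypothesis reads "The repellent samples are expected to provide 8 hours of personal protection from" the target species, and the sample-size rationale works from "an estimated among-subjects standard deviation of 2.0 hours at a 95% confidence level for an 8 hour protection time". Study Rationale describes earlier picaridin repellents as "efficacious against other species of mosquitoes in the laboratory as well as in field studies for up to and beyond 8 hours".

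For the times themselves, Data Analysis says: "These data will be aggregated and basic descriptive statistics determined (e.g., mean, standard deviation, confidence intervals". It expects negative skewness and answers it with a reflected log transformation. If skewness is significant, the median becomes the measure of central tendency. Intervals are then to be based on percentile ranks instead of standardized scores; the text does not make clear whether that applies to every interval or only to skewed data. A separate analysis gives the proportion of subjects without bites at each half-hour and plots a degradation curve.

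Nothing states how an arm without a confirmed bite at 8 h enters these summaries. The Fail Time row of the raw data sheet has no code for it.

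**The concern.** An arm with no First Confirmed Bite by 8 h has no observed protection time. All that is known is that its protection time exceeds 8 h. Similarly, a subject who leaves early contributes only a lower bound at the last bite-free exposure. Pooling such values with true failure times estimates something other than the mean protection time.

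The expected negative skew is what a block of tied values at the cut-off would produce. A transformation changes the scale of those ties but cannot supply the missing failure times.

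At stake is the stated objective, in a study meant to support a label claim. The point estimate would be too low and its precision overstated, and the problem grows as the product gets better.

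**Working it through.** **Inputs.** Cut-off 8 h (Testing); expected protection time 8 h (Hypothesis, sample-size rationale); SD 2.0 h and 10 treated subjects (sample-size rationale); 12 arms per product if both spare subjects are used (Experimental Design); half-hourly exposures (Testing). Two assumptions are not in the protocol: protection time T is Normal(8, 2), and unfailed arms are scored 8.0 h.

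**The plan's own figure.** The rationale gives 10 to 11 subjects but no interval half-width E, so it can only be back-solved from n = (1.96 × 2 / E)². E = 1.2 h gives 10.67 and E = 1.25 h gives 9.83. The figure can be neither confirmed nor refuted, and nothing below depends on it.

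**Share censored.** P(T > 8) = 0.50 per arm. P(at least one of 10) = 1 − 0.5¹⁰ = 99.9%.

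**Mean and SD of the recorded value, min(T, 8).**
- Mean = 8 − 2 × 0.3989 = 7.20 h, a bias of −0.80 h.
- SD = 2 × √(0.5 − 0.3989²) = 1.17 h, which is 42% below 2.0 h.
- With failures dated to the next half-hour exposure, simulation gives a mean of 7.32 h and an SD of 1.09 h.
- Dropping unfailed arms instead gives 8 − 2 × 0.3989 / 0.5 = 6.40 h, which is worse.

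**Coverage of 8 h by a nominal 95% t-interval (simulation).**

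| Arms | No grid | Half-hour grid |
|---|---|---|
| 10 | 54% | 67% |
| 12 | 36% | 51% |

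Without censoring, the interval with 10 arms covers in 95% of trials with half-width 1.39 h. With unfailed arms at 8.0 h (no grid) the half-width shrinks to 0.79 h. Measured against the mean restricted to 8 h, coverage with 10 arms is about 89%.

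**The other planned routes (10 arms, no grid unless stated).**
- Reflect-and-log: back-transformed centre 7.45 h; the interval covers 8 h in 39% of trials.
- Median: skewness is significant (|skew/SE| > 1.96) in about 50% of trials (59% on the grid), so the mean would still be reported in many.
- Percentile-rank interval for the median (2nd to 9th value): covers a median of 8 h in about 99% of trials, but its upper limit cannot exceed 8 h, so coverage is 0% at a true median of 9 h.

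**A better product.** At true means of 9 h and 10 h (SD 2 h), 69% and 84% of arms are censored, the recorded means are 7.60 h and 7.83 h, and t-interval coverage of the true mean is about 0%.

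**Smaller SD.** At a mean of 8 h and SDs of 0.5, 1.0 and 1.5 h, the recorded means are 7.80, 7.60 and 7.40 h. On the grid with 10 arms, t-interval coverage is 96% at SD 0.5 h and 82% at SD 1.0 h.

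**No arm fails.** The result is mean 8.0 h, SD 0 and every interval 8.0 to 8.0. The exact 95% lower limit for the proportion protected is only 0.025^(1/10) = 69% for 10 of 10, or 0.025^(1/12) = 74% for 12 of 12. With 10 arms the chance of this is 0.5¹⁰ ≈ 0.1% at a mean of 8 h, about 2.5% at 9 h and about 18% at 10 h.

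**Comparison.** A right-censored normal likelihood on the same kind of data (true mean 8 h, SD 2 h, 10 arms, no grid) returns on average 8.06 h and SD 1.89 h.

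**The case against.** Several points on the other side stand.

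- **The median route exists.** Data Analysis can be read as avoiding t-intervals altogether, and at least does so for skewed data, which it expects. A rank-based interval performs well for a median at or below 8 h. A reader might infer that every planned summary is invalid; the text does not support that.
- **Scoring at 8.0 h is an inference.** The protocol is silent on unfailed arms. Pooling all times into one mean makes 8.0 h the natural reading, and the expected negative skew fits it, but a reader should not conclude that the protocol prescribes this.
- **Normality is assumed.** The sample-size rationale gives 8 h and 2.0 h but no distribution, so the coverage figures are not the protocol's own.
- **The degradation curve does much of the work.** If nobody leaves early and failed arms stay counted as failed, it equals a Kaplan-Meier curve on the half-hour grid. It lacks an interval and a censoring rule.
- **The direction is conservative.** The mean is biased low, so this bias cannot by itself produce a false 8 h claim. Against the mean restricted to 8 h, the t-interval is only moderately short of nominal; most of the coverage loss comes from targeting the unrestricted mean.
- **The zero-width interval is rare** at the planning values, about 0.1% of trials with 10 arms.

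What remains is that the objective names the mean protection time without restriction, the cut-off equals the expected value, and no listed summary recognises censoring. A separate analysis plan could not cure this while the protocol itself fixes these summaries.

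**Conclusion.** The point holds as a defect that should be fixed. With expected protection equal to the cut-off, the mean protection time in the objective cannot be validly estimated by the summaries in Data Analysis.

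The figures rest on unfailed arms entered as 8.0 h and an assumed Normal(8, 2). On that basis the mean is about 0.7 to 0.8 h too low, the SD is about 1.1 to 1.2 h instead of 2.0 h, and coverage of 8 h with 10 arms is 54% to 67%. The coverage figures apply only to a t-interval for the unrestricted mean. The effect is milder with a smaller SD. The percentile-rank interval is sound for a median up to 8 h and uninformative above it.

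**What to change.** In Data Analysis, replace the sentences on mean, SD and transformation with a Kaplan-Meier estimate of time to First Confirmed Bite for each product, with arms lacking one right-censored at their last exposure (8 h or withdrawal). Add an exact 95% interval to the proportion protected at 8 h, which the degradation curve already yields. Report the median with its survival-based limits, printed as >8 h when not reached. If a mean is kept, label it as restricted to 8 h or take it from a censored-data model, and reword the Objective to match.

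The cost is about one paragraph of text and a standard procedure, with no extra subjects or data. The small downside is that the median will often read >8 h with no upper limit.
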